2. STUDY OBJECTIVES AND OUTCOMES

The study is made up of two parts, a phase 2 study to reconfirm the safety of the trial regimen, i.e. the combination of bedaquiline and rifampicin administered as a single dose, and a phase 3 study in which we will evaluate effectiveness of this regimen in preventing leprosy, compared to the standard WHO regimen consisting of a single dose of rifampicin only. Implementation of the phase 3 study will be

conditional upon the safety results of the phase 2 study. In addition will enroll leprosy patients diagnosed, as well as tuberculosis patients, to monitor resistance against the study drugs. We will also conduct a PGL-I sero survey in part of the study population for whom earlier PGL-I data are available to assess the potential of such surveys as a tool to monitor transmission of *M. leprae*. These sub-studies are an integral part of BE-PEOPLE because we need to be able to monitor whether resistance against the drugs used, bedaquiline and rifampicin, is emerging, from the earliest possible stages. Also we need to be able to assess whether post exposure prophylaxis has an impact not only on progression from infection to disease but on transmission as well; this requires a tool that needs to be validated.

2.1 Phase 2 study

2.1.1 Primary:

To confirm safety of the study regimens, single dose bedaquiline plus rifampicin and single dose rifampicin, in a field setting in Comoros

Outcome: Advice by DSMB on whether or not phase 3 trial can be implemented as foreseen in this protocol, taken into account QTc data, observed (S)AEs and predetermined stopping criteria.

2.1.2 Secondary

1. To determine the baseline frequency of ALT and AST elevations and QTc prolongations in the population.
2. To document for each of the two regimens post administration QTc levels, as well as any potentially frequent adverse events such as gastro-intestinal (nausea, vomiting), nervous system-related (headache, dizziness) and cutaneous reactions.

2.2 Phase 3 study

2.2.1 Primary

To evaluate effectiveness of PEP based on a combination of rifampicin and bedaquiline (BE-PEP), in preventing leprosy among contacts of incident cases.

Outcome: The incidence rate ratio of leprosy between contacts who received the trial regimen (BE-PEP: rifampicin 600 mg plus bedaquiline 800mg, repeated once after four weeks for household contacts) and those who received the WHO standard prophylactic regimen (SDR-PEP: rifampicin 600 mg, single dose).

2.2.2 Secondary

1. To assess effectiveness of the BE-PEP regimen at village level.

Outcome: The incidence rate ratio between villages that received BE-PEP and villages that received SDR-PEP.

2. To quantify frequency of potential adverse events such as gastro-intestinal (nausea, vomiting), nervous system-related (headache, dizziness) and cutaneous reactions.

Outcome: The proportion of participants treated with BE-PEP that report adverse events, with a breakdown by type of event.

3. To assess anti-PGL-I sero surveys as a tool to monitor leprosy transmission

Outcome: Age specific anti-PGL-I sero prevalence rates in villages belonging to arm 4 of the original PEOPLE trial at the time of the first survey round in 2019 and the final round of BE-PEOPLE in 2026

4. To monitor rifampicin and bedaquiline resistance among leprosy and tuberculosis patients

Outcome: We will quantify the prevalence of rifampicin and/or bedaquiline resistant strains of *M. leprae* and *M. tuberculosis* on each of the study islands making use of molecular markers.

5. To assess cost-effectiveness of the BE-PEP regimen compared to SDR-PEP.

Outcome: Cost per case averted between BE-PEP arm and SDR-PEP.

3. STUDY DESIGN

3.1 General study design

We will conduct a phase 3 intervention trial comparing the effectiveness of two different regimens of post exposure prophylaxis for leprosy. Because we will be using a new drug (bedaquiline) that has not been used before for this indication, we have planned a phase 2 safety study to start in July, 2022. For this study we will select a small village (Gégé, Anjouan) that is part of the comparator arm of the PEOPLE trial and in which to date eight leprosy cases were diagnosed but that will not be included in the BE-PEOPLE trial because of its small population size (n=908). In this village, in May 2022, we will conduct the final round of door-to-door screening for leprosy in the framework of the PEOPLE trial. All cases identified will be treated in accordance with the national standards. Upon completion of screening, a random sample of 150 participants not meeting the exclusion criteria will be offered BE-PEP with strict monitoring for adverse events, in particular ECG and liver function will be monitored pre- and post-drug administration. The remainder will receive single dose rifampicin (SDR-PEP), as per WHO recommendation. Of those a random sample of 150 will also be subjected to the same procedures for monitoring adverse events as those receiving BE-PEP. Results will be presented to an independent data safety management board and the regulatory authority in the Comoros who will then decide whether or not the main phase 3 trial can go ahead. The full BE-PEOPLE study is expected to run from January, 2022 until 4 year follow-up is finished in all phase 3 participating villages (expected by the start 2027) A Gantt chart of the main project activities is presented in figure 2 below.

The BE-PEOPLE study is a follow-up to the ongoing PEOPLE study, in Comoros only. Baseline screening will take place in 2022 and the beginning of 2023, partially overlapping with the final screening round of PEOPLE. We will then re-randomize 34 out of 48 villages that were already part of PEOPLE as well as 10 new clusters to two new study arms: arm 1 in which BE-PEP i.e. bedaquiline (400 or 800 mg depending on weight band) combined with rifampicin (10 mg/kg) will be provided as post-exposure prophylaxis, and arm 2 in which only SDR-PEP (rifampicin 10 mg/kg) will be provided. Anyone living within 100 meters of an index case (PEP zone) will be eligible for PEP. In case 50% of the village population or more lives within 100 meters of an index case the PEP zone will be extended to the entire village. For the first PEP distribution at village level any leprosy case included in the study population detected during the annual village screening or in the preceding five-year period, i.e. since January 1st, 2018 will be considered an index case. The following years, any leprosy case detected after the last year's screening up to and including the village's screening round of the current year will be considered an index case.

Annual village screening rounds will take place for 4 years starting in 2023. When annual screening is completed in a village, a list of eligible households (based on the PEP zone) will be elaborated followed up with PEP intervention to those individually eligible based on annually evaluated inclusion and exclusion criteria listed in the protocol. If a participant whose village is randomized to the BE-PEP arm, is individually ineligible for BE-PEP, but individually eligible for SDR-PEP, the participant may receive

SDR-PEP. Because there has been no distribution of PEP during the final PEOPLE survey round in 2022, all participants will in principle be eligible again for PEP when the BE-PEOPLE intervention starts in 2023.

The final screening round will take place 4 years after the first screening round in 2023 and will in a subset of villages (those that belonged to arm 4 of PEOPLE) be followed by a serological survey (PGL-I) aimed at measuring prevalence of infection with *M. leprae*.

Year 2	Phase 3 study	Screening Arm 1 & 2 + PEP intervention	Sampling leprosy patients	Sampling TB patients	
Year 3	Phase 3 study	Screening Arm 1 & 2 + PEP intervention	Sampling leprosy patients	Sampling TB patients	
Year 4	Phase 3 study	Final screening Arm 1 & 2	Sampling leprosy patients		PGL-I survey

Table 1: Time table BE-PEOPLE

Participants in the new villages will be asked for informed consent for baseline screening in 2022. Informed consent for the phase 3 intervention trial will be asked during the first intervention round in 2023, when we know to which study-arm villages have been randomized. Informed consent for the leprosy patient cohort will remain separate, the same applies to the TB patients being enrolled. For the PGL-I survey in 2026, separate informed consent will be asked ahead of the survey.

Figure 1 below shows how villages belonging to the various arms of PEOPLE will merge into BE-PEOPLE. We have dropped some villages that had a low incidence so far during the PEOPLE trial or a small population size. To arrive at the required sample size we will also include nine new villages, eight on Anjouan and one on Mohéli, the latter to be split into two clusters. Villages will be arranged by PEOPLE study arm and by island in order of decreasing prevalence during the 2022 baseline survey and regrouped into pairs. Within each pair they will be randomized to arm 1 or arm 2 of BE-PEOPLE.

[figure not shown]

Figure 1: Inclusion and randomization BE-PEOPLE (Phase 3) trial

The main outcome measure of BE-PEOPLE will be the incidence rate ratio of leprosy between individuals in arm 1 who received BE-PEP and individuals in arm 2 who received SDR-PEP, controlled for potential confounding by distance to nearest index case at baseline, as well as for contextual confounding through the use of a random effects model (village nested within island). To avoid a potential selection bias, those who received SDR-PEP but would not have been eligible for BE-PEP, i.e. children below the age of 5 or with a weight below 20 kg, will be excluded from this analysis. Details are described in chapter 9, 'Data analysis'.

We will make optimal use of the setup created in the PEOPLE project with five survey teams on the island of Anjouan and two on the island of Mohéli that have recorded and georeferenced all study participants to date in the PEOPLE trial (> 85,000). In addition, on both islands there are central teams that supervise activities in the field, confirm leprosy suspects identified, sample leprosy patients for molecular confirmation, and supervise their treatment.

Immediately following the final round of door-to-door screening of BE-PEOPLE a PGL-I survey will be conducted covering eight villages that originally were part of arm 4 of the PEOPLE trial (n = 17,000), with the aim of comparing age specific seroprevalence rates to those at baseline of PEOPLE, in 2019. The purpose of this comparison is to assess whether anti-PGL-I surveys have potential as a tool to monitor leprosy burden and -transmission. Earlier studies in Indonesia and Brazil have shown mixed results. [27, 28]

Detailed records on costs will be maintained allowing an assessment of cost effectiveness of BE-PEP compared to SDR-PEP.

Figure 2 below shows a Gantt chart of all activities planned throughout the project.

Figure 2: Gantt chart of the BE-PEOPLE trial

Activity	2022					2023				2024				2025				2026				2027			
	Q4	Q1	Q2	Q3	Q4	Q1	Q2	Q3	Q4	Q1	Q2	Q3	Q4	Q1	Q2	Q3	Q4	Q1	Q2	Q3	Q4	Q1	Q2	Q3	Q4
1. Obtaining ethics and administrative approval for study protocol	x																								
2. Finalizing study procedures	x	x																							
3. Conduct Phase 2 study			x	x	x	x																			
4. Go no-go decision for phase 3 based on advice of DSMB							x																		
5. Obtain green light from authorities in Comoros for phase 3							x																		
6. Baseline survey BE-PEOPLE (overlaps with final survey of PEOPLE in 32 villages)			x	x	x	x																			
7. Randomization BE-PEOPLE arm 1 and 2								x																	
8. First Leprosy screening round BE-PEOPLE, Provide SDR-PEP and BE-PEP							x	x	x	x															
9. Second Leprosy screening round BE-PEOPLE, Provide SDR-PEP and BE-PEP											x	x	x	x	x										
10. Third Leprosy screening round BE-PEOPLE, Provide SDR-PEP and BE-PEP											x	x	x	x	x										
11. Final Leprosy screening round BE-PEOPLE																			x	x	x	x	x	x	
12. Continue sampling of incident leprosy patients	x	x	x	x	x	x	x	x	x	x	x	x	x	x	x	x	x	x	x	x	x	x	x	x	
13. Sampling incident tuberculosis patients						x	x	x	x	x	x	x	x	x	x	x	x	x	x	x	x	x	x	x	
14. Collect costing data						x	x	x	x					x	x	x	x	x	x	x	x				
15. Analyze costing data									x	x													x	x	
16. Anti-PGL-I testing of former arm 4 villages																		x	x	x	x				
17. Interim analyses										x				x			x		x						
18. Cost effectiveness analysis																							x	x	
19. Final analysis on effectiveness of BE-PEP																						x			

4. PARTICIPANTS, POPULATION & SELECTION

4.1 Study settings

The study takes place in Comoros, an island nation in the Indian ocean, just north of Madagascar. We will build on the existing setup of the PEOPLE trial on the islands of Anjouan and Mohéli. In Comoros the national leprosy and tuberculosis control program (NLTCP) provides free diagnostic and treatment services for both diseases, in accordance with international standards. The NLTCP is supported by Damien Foundation, an international NGO with headquarters in Brussels, Belgium. In Comoros the leprosy burden is concentrated on two of the three islands, Anjouan and Mohéli. On the main island, Grande Comore, only sporadic leprosy cases are reported, with higher notifications of tuberculosis. Rifampicin resistant tuberculosis is exceedingly rare, and has not yet been observed since introduction of universal Xpert MTB/RIF testing in 2017. Patients with skin conditions can present at public health centers where they are examined by general health services staff who have been trained in diagnosing and treating leprosy. They are supervised by staff from the NLTCP, to whom they can also refer patients for consultation. Specific treatment for leprosy is provided free of charge, either directly or through the primary healthcare system. In addition outreach campaigns at village level are organized in which persons with skin conditions are invited to present themselves for screening. Free treatment is provided for minor skin conditions and any leprosy patient diagnosed receives full treatment. Such outreach campaigns, also called 'mini-campaigns' have been introduced in Comoros since 2008. For the BE-PEOPLE trial, door-to-door screening activities will be carried out by teams that were established in the framework of the PEOPLE study which will be complemented by several new teams, under the direct supervision of the NLTCP and under responsibility of the country PI. The teams will receive the necessary protocol and (refresher) GCP training prior to the start of the BE-PEOPLE study. They will also receive training on aspects of concomitant medication. Any leprosy patients identified will be treated according to the national guidelines of Comoros, which are in accordance with WHO guidelines.

4.2 Study population and selection criteria

For the phase 2 study we have selected the village of Gégé, a leprosy endemic village on the island of Anjouan at one hours' driving distance of the main hospital in the capital. The village has an estimated population of approximately 900 and is currently part of arm 1 of PEOPLE, the comparator arm. Therefore no PEP has been provided yet although 8 leprosy cases were diagnosed during the PEOPLE trial so far. The village will be screened once more in the framework of the PEOPLE trial, in May, 2022. After this final screening, BE-PEP and SDR-PEP will be provided for the phase 2 study of BE-PEOPLE. The village will not be part of the phase 3 study of BE-PEOPLE. A random sample of 150 eligible participants will receive BE-PEP, the remainder will receive SDR-PEP. Those receiving BE-PEP as well as a random sample of 150 among those receiving only SDR-PEP will be strictly monitored for adverse events. As an additional safety measure BE-PEP administration will start with adults 18 years and older, followed by children aged 13-17, and finally children aged 5-12. Provision of BE-PEP to children aged 13-17 will start once post BE-PEP QTc measurements for adults are available and have shown no indication for concern, similarly distribution to children aged 5-12 will start once post BE-PEP QTc measurements for children aged 13-17 are available and show no reasons for concern.

Inclusion and exclusion criteria for the phase 2 study will be the following:

Inclusion criteria:

1. Being a permanent resident of the study village, in good state of health
2. Able and willing to provide informed consent
3. Age 5 years or above and weight of 20 kg or above.

Exclusion criteria

1. Signs of active leprosy
2. Signs of active pulmonary tuberculosis (cough ≥ 2 weeks duration)
3. Signs of active extra-pulmonary tuberculosis (bluish-red nodules that cover the lymph nodes, bones or joints, or cervical glands with discharge)
4. History of liver- or kidney disease
5. Allergy to rifampicin or bedaquiline
6. Having received rifampicin or bedaquiline (if applicable) in the last 2-year period
7. Not able to swallow bedaquiline 100 mg tablets
8. Self-reported (suspected) pregnancy or breastfeeding
9. Concurrent (within the last three week period before D0) use of medications not included in the safe list (for bedaquiline only)
10. QT-prolongation of ≥ 450 msec in baseline ECG within the last week.

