4.4 Randomization

For the phase 2 safety study we will first complete the final survey round of the PEOPLE study and then enumerate all those aged 5 years or above, weighing 20 kg or above and not currently suffering from leprosy. They will be divided into three age categories, 5-12 years, 13-17 years, and 18 years and above. We will then determine the overall proportions of the three age groups, the proportion multiplied by 150 will be the number of participants to be recruited per study arm for each age group. Next we will prepare sealed envelopes containing a note indicating either BE-PEP or SDR-PEP as PEP regimen, 300 in total. They will be divided into three groups with equal numbers per PEP regimen, one group of envelopes for each of the three age categories.

The next step will be to enroll the required numbers of adults (age 18 years and above) by visiting the households one by one and inviting eligible subjects to be enrolled. Each time a person agrees, an envelope will be drawn and either SDR-PEP or BE-PEP will be provided as indicated on the note inside the envelope. This process will continue until all envelopes for adults have been allocated. Provided no concerning adverse events are observed, the procedure will be repeated for the 13-17 years old. Again if no concerning adverse events are observed, the 5-12 years old will be enrolled following the same procedure. The remainder of the village population aged 2 years and above and not meeting other exclusion criteria will then be offered SDR-PEP.

Randomization for study arms 1 and 2 of the phase 3 study, will take place upon completion of the baseline survey. We will then arrange all villages by island and by group (former arm 1, 2, 3 or 4 or new villages), in order of decreasing prevalence. As was explained earlier, Fomboni, the capital of Mohéli, will be split into two clusters. Thus we will arrive at 22 pairs of clusters. Blocked randomization will be used to allocate clusters into the two study arms. The randomization schedules will be prepared by an independent sponsor biostatistician. The randomization list will be prepared using SAS 9.4 (SAS Institute, Cary NC).

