5. STUDY PROCEDURES

5.1 General Study Procedures

The study has been planned in two phases. The main, phase 3 study will be preceded by a phase 2 study in the village of Gégé on Anjouan. In this village we will conduct door-to-door screening for leprosy in May, 2022, coinciding with the final screening round of the PEOPLE study. We will then ask for informed consent for inclusion in the phase 2 study of BE-PEOPLE. To those who consent we will provide post exposure prophylaxis with BE-PEP or SDR-PEP with intensified safety monitoring, as was described in chapter 4.4 above. Safety monitoring will include an ECG taken less than 1 week before treatment and approximately 24 hours after treatment, as well as liver function tests less than 1 week before and 14 days after treatment. In case of an ALT/AST elevation adverse event on visit D14 or absolute AST/ALT value increase of ≥ 35 between the prerecruitment visit and visit D14, liver function tests will also be included on visit D30. The team, including a medical doctor will be present during the PEP administration round (=D0), as well as the day after (=D1) to collect safety data (including QTc). The team, again including a medical doctor, will investigate the participant at the study center 14 days after (=D14) to collect additional safety data (ALT + AST) and to follow up on any ongoing (S)AE's. In case any SAE's are ongoing during the visit on D14 additional visits will be organized to follow up. A final visit to collect adverse events will be organized on D30 at the participant's house. In case liver function tests are necessary on visit D30, the participant will be invited to the study house for visit D30.

In case of any serious adverse events, transport to the hospital in the island capital Mutsamudu will be ensured, where cardiological care is provided including monitoring, electrolyte correction, and cardiac resuscitation. A project vehicle will be on standby in the village for this purpose. The results of this phase 2 safety study will be presented to the data safety monitoring board (DSMB), involved ethical committees, and local regulatory authority who will provide an opinion on whether or not the green light can be given for the main phase 3 study.

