## 2. Study design and objectives

### 2.1. Study design

This is a single-site, randomized, non-inferiority, phase 2 clinical trial, comparing the safety between a single dose rifampicin (SDR-PEP) and single dose bedaquiline plus rifampicin (BE-PEP) among contacts of recent leprosy cases. Safety will be closely monitored and evaluated by an independent data and safety monitoring board (DSMB). The study setting is the village of Gégé, Anjouan, that is part of arm 1 of the PEOPLE trial in which 8 new cases have been diagnosed since 2019 but no PEP has been provided.

During the final survey round of the PEOPLE study, all individuals in the village aged 5 years or above, weighing 20 kg or above and not currently suffering from leprosy will be enumerated and screened for the study inclusion and exclusion criteria (see 5Description of analysis populations Description of analysis populations for more details).

Three hundred of the eligible individuals from the village will be stratified proportionally over three age-groups (18 years and above, 13-17 years, and 5-12 years) and will be randomized (1:1) into one of the two study arms:

- Arm 1: single dose of bedaquiline plus rifampicin (BE-PEP) (n=150)
- Arm 2: single dose of rifampicin (SDR-PEP) (n = 150)

Randomization will occur sequentially, first enrolling persons above 18 years of age. Provided no concerning adverse events are observed, the randomization and enrollment will continue for the 13-17 years old age category. Again if no concerning adverse events are observed, the enrollment will proceed for children aged 5-12 years old. The remainder of the population of this village aged 2 years and above will be offered single dose rifampicin as per WHO recommendations.

All randomized participants will be followed up closely with active monitoring for adverse events, including measurement of the corrected QT interval and liver function, before and after administration, as well as any other adverse events, including but not limited to gastro-intestinal (nausea, vomiting), nervous system-related (headache, dizziness) and cutaneous reactions.

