### **6.4. Interim analysis**

An interim analysis will take place after the completion of recruitment of each age stratum. Data will be cleaned and locked before each interim analysis. The data will include any results until day 30.

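### Phase 2 age escalation: the stated gate to each younger stratum does not wait for the older stratum's day-14 ALT/AST (minor; cheap to fix)

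*Protocol*

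**What the plan says.** Phase 2 doses adults first, then ages 13-17, then ages 5-12. The rule for moving down a stratum appears in several places.

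- **Protocol 4.2.** The 13-17 stratum "will start once post BE-PEP QTc measurements for adults are available and have shown no indication for concern". The 5-12 stratum follows "once post BE-PEP QTc measurements for children aged 13-17 are available and show no reasons for concern".
- **Protocol 4.4.** "Provided no concerning adverse events are observed, the procedure will be repeated for the 13-17 years old", and the 5-12 stratum has the matching sentence: "Again if no concerning adverse events are observed, the 5-12 years old will be enrolled following the same procedure".
- **SAP 2.1.** "Provided no concerning adverse events are observed, the randomization and enrollment will continue for the 13-17 years old age category".
- **Protocol 4.3.** Adult outcomes receive a preliminary assessment before minors are enrolled. Which outcomes, and at what time, is not said.
- **SAP 6.4.** "An interim analysis will take place after the completion of recruitment of each age stratum". On content: "The data will include any results until day 30". The data are to be cleaned and locked first. No link to enrolment is made.

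The assessments fall at different times. Protocol 5.1 takes the post-dose ECG at about 24 hours but schedules "liver function tests less than 1 week before and 14 days after treatment". Table 2 gives D14 a window of 2 days either side. Protocol 8 adds rules that pause enrolment at any moment, including one unexplained AST or ALT above 8 times the upper limit of normal.

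**The concern.** The age staircase exists so that safety is seen in older participants before healthy minors receive the combination. The annexed regulatory advice names cardiovascular and hepatic safety as the major issues and recommends a phase 2 with both ECG and liver enzyme monitoring. The explicit condition in 4.2 names only the cardiac part. The adverse-event condition can include liver findings, because the protocol treats an ALT/AST elevation as an adverse event and SAP 6.3 groups such events into a category. But an event can only be observed once the blood has been drawn, and the first scheduled post-dose draw is at D14. A gate that can be satisfied at D1 can therefore open before part of the liver evidence exists. A liver signal arriving later would still pause enrolment if it met a pause criterion, but possibly after some younger participants had been dosed.

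**Working it through.** **1. Is there a waiting rule?** Set side by side, 4.2 requires D1 QTc; 4.4 and SAP 2.1 require no concerning adverse events so far; 4.3 requires a preliminary assessment without content or date; SAP 6.4 requires an analysis but not a hold. Protocol 8 describes DSMB review when phase 2 is finished or after a pause, not between strata. None makes the next stratum wait for D14 ALT/AST.

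**2. Length of the gap.** For the last participant in a stratum: D14 - D1 = 14 - 1 = 13 days. With the window: 12 - 1 = 11 to 16 - 1 = 15 days.

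**3. Results outstanding.** The plan gives no accrual pace, so the paces below are assumptions. Inputs: about 75 adults and 75 minors on BE-PEP (4.3); r = BE-PEP participants dosed per day; gate opens on D1 of the stratum's last participant; no time for ECG reading or laboratory work. The size m of the 13-17 stratum is not given. Spreading ages 5-17 evenly gives 75 x 5/13 = 28.8, taken as 29, which leaves 46 aged 5-12. The slowest pace spreads 150 BE-PEP participants over 365 days: r = 150/365 = 0.41.

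- Adults outstanding when 13-17 opens = min(75, 13r); range from 11r to 15r.
- Share of 13-17 results in hand when 5-12 opens = max(0, 1 - 13r/m).
- Children aged 5-12 who could be dosed before the last 13-17 result = min(46, 13r).

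| r per day | Accrual (150/r) | Adults outstanding of 75 (window) | Adult results in hand | 13-17 results in hand (m = 29) | Children 5-12 dosed before last 13-17 result |
|---|---|---|---|---|---|
| 0.41 | 365 days | 5 (5-6) | 93% | 82% | 5 |
| 1 | 150 days | 13 (11-15) | 83% | 55% | 13 |
| 2 | 75 days | 26 (22-30) | 65% | 10% | 26 |
| 3 | 50 days | 39 (33-45) | 48% | 0% | 39 |
| 5 | 30 days | 65 (55-75) | 13% | 0% | 46 |

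If m is 20 or 35 instead of 29, the 13-17 share in hand is 35% or 63% at r = 1, and 0% or 26% at r = 2.

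The Gantt chart marks four quarters for phase 2 (the table extraction may be imperfect), so the slow rows are at least as plausible as the fast ones. Each day spent reading ECGs before the gate opens shortens the 13 days by one.

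**4. What waiting would buy.** Suppose, as an assumption only, a true liver event rate of 2% on BE-PEP. The chance of seeing at least one event among n results is 1 - 0.98^n. With all 75 adults it is 78%; with 70 in hand (one-year accrual) 76%; with 62 (r = 1) 71%; with 10 (r = 5) 18%. At slow accrual the loss is small; at fast accrual it is large.

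**The case against.** The strongest reply is that SAP 6.4 already is the gate. An interim after each sequential stratum, on locked data to day 30, has little other natural purpose, and 4.3 says that adult outcomes are assessed first. SAP 3.1.2 lists post-dose ALT and AST among the outcomes. If that was the intention, all D14 results would be in hand. This may well be so, but it is an inference: 6.4 does not mention enrolment, and 4.2 states a rule that is met earlier.

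Second, gating on QTc is a reasoned choice. The annexed advice reports that the QTcF change after a single 800 mg dose peaked at 16 hours, so a 24-hour reading targets the acute risk. It rates overlapping hepatic toxicity as of more limited importance because it is usually seen after multiple doses. It asks only for a minimum number of adults first, whereas the protocol completes each whole stratum. All of this stands and limits the severity.

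Third, liver protection exists: exclusion above 3 times the upper limit at baseline, testing at D14 with triggered testing at D30, and the pause rules. These also stand, though the pause rules act only on results already available.

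Three stronger readings are tempting and unsupported. A reader might infer that the gate ignores liver findings; it does not, since a concerning elevation already known counts as an adverse event. A reader might infer that minors would be dosed with no liver data from older participants; incomplete is the right word, and zero 13-17 results arises only above about 29/13 = 2.2 BE-PEP participants per day. A reader might infer that the regulatory advice was breached or that early dosing occurred; the advice asked for no liver gate, and the documents show what the text permits, not what was done.

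**Conclusion.** The point holds as a modest gap in the wording of the escalation rule. Followed literally, the plan lets a younger stratum open 11-15 days before the older stratum's last scheduled liver result. The 13-day figure follows directly from the visit schedule. The counts do not: they rest on assumed paces, an assumed size for the 13-17 stratum, and a gate that opens as soon as D1 is reached, which is the least favourable timing. Under those assumptions between about 5 and 65 of 75 adults would be outstanding at the first step. The second step is the weaker one at the faster paces, because the 13-17 stratum is small. No rate of liver harm is given in the documents, so no excess harm can be calculated. Severity is minor: this is a cheap safety improvement, not a flaw that undermines phase 2.

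**What to change.** State in Protocol 4.2 and 4.4 and in SAP 2.1 and 6.4 that the next stratum opens only after the older stratum's D1 QTc, D14 ALT/AST and adverse events to D14 have been reviewed and no pause criterion is met. Align SAP 6.4 with this: say either that its interim informs escalation, or that the D14 review is the gate and the day-30 interim is a later summary.

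Cost: wording in four places, and about 13 days plus laboratory turnaround at each of two steps, so 2 x 13 = 26 days in total (22-30), which is small against the four quarters marked for phase 2. Using the day-30 interim as the gate would take longer: 30 - 1 = 29 days per step, before data cleaning. No visits or tests are added, provided the minors' baseline ECG and ALT/AST, which must fall within a week of dosing, are scheduled after the gate opens.

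If phase 2 enrolment is already complete, the phase 2 report should state which liver results were in hand when each younger stratum opened.
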